##### 5.3.2.2 Exposure

If the start of treatment date is missing, the latest possible date of all the pre-dose assessments, up to and including Randomization will be imputed as the start of treatment date.

---

Document:

C:\ProgramData\activePDF\Temp\DocConverter\API\Input\\$651f4dc0b253\$FE3041C5883446E892B20AB6D3F0E1BD.docx

Author: [name]

Version and Date: Version 1.0, 21 Apr 2023

Page 53 of 66

If the end of treatment date is missing, the latest possible time of all the post-dose assessments will be imputed as the end of treatment date.

### **5.3.2.3 Adverse Events**

Missing and/or incomplete dates/times for AEs are imputed in a manner to ensure a conservative approach to treatment period if the missing/partial dates cannot definitively exclude the treatment period, taking additionally into account that the start date/time should not be after the stop date/time. Stop dates/times will not be imputed if the AE is ongoing.

This will be done as follows:

When the day of onset of an AE is missing:

- If month and year of onset of an AE is the same as the month and year of date of first administration of the study drug, then the missing day is imputed as the day of date of first administration of the study drug.
- Otherwise, the missing day is imputed as 1st of the month.

When the day and month of onset of an AE are missing:

- If the year of onset of an AE is the same as the year of date of the first administration of the study drug, then the missing day and month are imputed as the day and month of date of first administration of the study drug.
- Otherwise, the missing day and month are imputed as January 1st.

If onset date is completely missing:

- If AE end date is on/after the date of first administration of the study drug, then onset date is set to date of first administration of the study drug.
- If AE end day or month are missing, then day will be imputed as last day of the month and month will be imputed as December:
  - If imputed end date is on or after the date of first administration of the study drug, then onset date is set to date of first administration of the study drug and AE is considered as treatment emergent.
  - If AE end date is prior to the date of first administration of the study drug, then onset date is not imputed, and AE is not considered as treatment emergent.

The imputation method will only be used to determine treatment emergence and to determine the time of the event relative to the first administration of study medication.

A worst-case approach will be followed in the event of missing intensity or causality data. If the intensity is missing, 'Severe' will be imputed. If causality data is missing, 'Related to study medication' will be imputed.

In the event that no coding information is available for a specific AE, the AE will be presented as an 'Uncodable Event' in summary tables.

### **5.3.2.4 Concomitant Medications**

Missing concomitant medication dates will be handled in a similar fashion as described for AEs in Section 4.3.6.

---

Document:

C:\ProgramData\activePDF\Temp\DocConverter\API\Input\\$651f4dc0b253\$FE3041C5883446E892B20AB6D3F0E1BD.docx

Author: [name]

Version and Date: Version 1.0, 21 Apr 2023

Page 54 of 66

## 5.4 Windowing Conventions

Table 19 presents the visit windows that will be used to assign assessments to a nominal visit.

**Table 19 Visit Windows**

Stage	Group	Visit	Visit Label	Visit Day	Visit Window
Screening	1 and 2	V1 – Screening (D -6 to -1)	Screening	Day -6 to -1	Day -6 to -1
1	1 and 2	V2 – Day 0	Baseline	0	
1	1 and 2	V3 – Day 1	D1	1	
1	1 and 2	V4 – Day 2	D2	2	
1	1 and 2	V5 – Day 3	D3	3	
1	1 and 2	V6 – Day 4	D4	4	
1	1 and 2	V7 – Day 7	D7	7	
1	1 and 2	V8 – Day 10	D10	10	±1 day from planned day
1	1 and 2	V9 – Day 12	D12	12	±1 day from planned day
1	1 and 2	V10 – Day 14	D14	14	±1 day from planned day
1	1 and 2	V11 – Day 21	D21	21	±1 days from planned day
2	1 and 2	V12 – Day 28	D28	28	±3 days from planned day
2	1 and 2	V13 – Day 35	D35	35	±3 days from planned day
2	1 and 2	V14 – Day 42	D42	42	±3 days from planned day

Document:

C:\ProgramData\activePDF\Temp\DocConverter\API\Input\\$651f4dc0b253\$FE3041C5883446E892B20AB6D3F0E1BD.docx

Author: [name]

Version and Date: Version 1.0, 21 Apr 2023

Page 55 of 66

**Statistical Analysis Plan**

Antev Ltd

Protocol Number: ANT-1111-02

**Quantitate**

The Clinical Data Experts

2	1 and 2	V15 – Day 77	D77	77	±3 days from planned day
2	1 and 2	V16 – Day 84	D84	84	±3 days from planned day
2	1 and 2	V17 – Day 119	D119	119	±3 days from planned day
2	1 and 2	V18 – Day 126	D126	126	±3 days from planned day
2	1 and 2	V19 – Day 161	D161	161	±3 days from planned day
2	1 and 2	V20 – Day 168	D168	168	±3 days from planned day
3	2 only	V21 – Day 203	D203	203	±3 days from planned day
3	2 only	V22 – Day 210	D210	210	±3 days from planned day
3	2 only	V23 – Day 217	D217	217	±3 days from planned day
3	2 only	V24 – Day 224 b	D224 b	224 b	±3 days from planned day
3	2 only	V25 – Day 231	D231 b	D231 b	±3 days from planned day
3	2 only	V26 – Day 238	D238 b	D238 b	±3 days from

Document:

C:\ProgramData\activePDF\Temp\DocConverter\API\Input\\$651f4dc0b253\$FE3041C5883446E8  
92B20AB6D3F0E1BD.docx

Author: [name]

Version and Date: Version 1.0, 21 Apr 2023

Page 56 of 66

						planned day
3	2 only	V27 – Day 245	D245 b	D245 b	±3 days from planned day	
3	2 only		D252	D252	±3 days from planned day	
Follow-up		1 and 2 (not entered in Stage 3 a )	V21 – 28 days after last dose	Follow-up	28 days after last dose	±3 days from planned day
Final Assessment		2 only (entered in Stage 3)		Final Assessment	1 week after last Stage 3 visit or >28 days after last injection for EW	

a Subjects not entered in Stage 3 will have follow-up, Subjects who entered stage 3 will have final assessments.

b Subjects should attend on Day 203 and every 7 days until Day 252 or until serum T levels are > 1 ng/mL (local lab result).

## 5.5 Schedule of Events

The Study Day of an event/assessment will be calculated relative to the first study medication administration at Baseline. The Study Day of events/assessments occurring before, at or after the first administration will be calculated as follows:

Study Day = (Date of event/assessment - Date of first study medication administration)

---

Document:

C:\ProgramData\activePDF\Temp\DocConverter\API\Input\\$651f4dc0b253\$FE3041C5883446E892B20AB6D3F0E1BD.docx

Author: [name]

Version and Date: Version 1.0, 21 Apr 2023

Page 57 of 66

## **6. Statistical Analyses**

Both Group 1 and Group 2 outputs will be displayed and analysed separately. Combined totals of the groups will be displayed for completeness, but not analysed.

### **6.1 Subject Disposition**

Subject Disposition will be summarized by absolute counts (n) and percentages (%). Percentages will be based on the number of subjects with data. Percentages will not be provided for number of patients enrolled; only the total number of subjects enrolled will be presented. The number of subjects who completed the study, the number of subjects who prematurely discontinued, number of subjects screened but not enrolled (Screen Failures), and the primary reason for withdrawal will be reported. The absolute counts (n) and percentages (%) will be presented for Safety set, Intention-to-treat set, and Per-protocol set.

### **6.2 Protocol Violations**

Protocol Violations will be summarised by absolute counts (n) and percentages (%). Percentages will be based on the number of subjects with data.

### **6.3 Demographics**

Demographics include collected and derived, continuous and categorical variables. Categorical variables will be summarised by absolute counts (n) and percentages (%) and continuous variables will be summarised as specified in Section 5.1.25.1.2.

### **6.4 Prostate Cancer Diagnosis**

Prostate cancer diagnosis, Gleason Score and TNM will each be summarised in a separate table. Qualitative parameters will be summarised by absolute counts (n) and percentages (%). Percentages will be based on the number of subjects with data.

### **6.5 Medical History**

Medical History will be listed only.

### **6.6 Prior and Concomitant Medication**

Prior medications and concomitant medications will be summarised separately. Both will be summarised by absolute counts (n) and percentages (%). Percentages will be calculated based on the number of subjects at risk for the specific treatment group. ATC Code Levels 2 and 4 and associated Preferred Terms will be presented.

### **6.7 Treatment Compliance**

Treatment Compliance includes derived continuous and categorical variables. Continuous variables will be summarised by the number of subjects, minimum, median, mean, SD, and maximum.

Compliance will be calculated as the percentage separately for Intramuscular and Subcutaneous, the formula to be used is:

Compliance = (Number of dose administered / Number of dose planned) x 100%

---

Document:  
C:\ProgramData\activePDF\Temp\DocConverter\API\Input\\$651f4dc0b253\$FE3041C5883446E8  
92B20AB6D3F0E1BD.docx

Author: [name]

Version and Date: Version 1.0, 21 Apr 2023

Page 58 of 66

## 6.8 Efficacy Analyses

The efficacy endpoints will include collected and derived, continuous and categorical variables. Continuous variables will be summarised as detailed in Section 5.1.2.

The primary analysis will be performed on the per-protocol (PP) population. In addition, a sensitivity analysis will be prepared in the intention-to-treat (ITT) population. All efficacy assessments on the PP population will be repeated for the ITT population.

The primary analysis is carried out on the PP population as there is no comparator and therefore no risk of bias towards one group. Also, due to the study design, it is not expected that there will be many protocol violations. Furthermore, it is not preferable for subjects who fail to attend the Day 28 visit to get their test to be included as non-responders in the primary response rate. If the response rate is below 90% in the ITT population but above in the PP, this will be considered in the interpretation of the results.

The following SAS code chooses the exact/Clopper-Pearson CI for the proportion of responders with two possible ways of extracting the data.

```
ods output binomialcls=<data out1>;
proc freq data=<data in> order= formatted; /* choose the correct order
option to specify which is the responder. See SAS documentation for
further details if required */
  table <responder variable> / bin(cl=exact);
  output out=<data out2>(keep=_bin_ xl_bin xu_bin) bin ;
run;
ods output close;
```

### 6.8.1 Primary Efficacy Analysis

Proportion of participants achieving castration level with serum T <0.5 ng/mL or 1.73 nmol/L at Day 28.

Descriptive statistics, including proportion, Clopper-Pearson confidence interval (CI), and absolute frequencies will be calculated

#### Sensitivity Analyses on Primary Endpoint

Proportion of participants achieving castration level with serum T <0.5 ng/mL or 1.73 nmol/L at Day 28 will be repeated on the ITT analysis set as a sensitivity analysis for the Primary endpoint.

### 6.8.2 Secondary Efficacy Analyses

1. Proportion of participants achieving castration level with serum T <0.2 ng/mL or 0.6394 nmol/L at Day 28 will be analysed as mentioned in the Section 5.1.2 for both ITT and PP Population.
2. Proportion of participants achieving castration level with serum T <0.5 ng/mL or 1.73 nmol/L at Day 42 will be analysed as mentioned in the Section 5.1.2 for both ITT and PP Population.
3. Proportion of participants achieving castration level with serum T <0.2 ng/mL or 0.6394 nmol/L at Day 42 will be analysed as mentioned in the Section 5.1.2 for both ITT and PP Population.

---

Document:

C:\ProgramData\activePDF\Temp\DocConverter\API\Input\\$651f4dc0b253\$FE3041C5883446E892B20AB6D3F0E1BD.docx

Author: [name]

Version and Date: Version 1.0, 21 Apr 2023

Page 59 of 66

4. Proportion of participants achieving castration level with serum T <0.5 ng/mL or 1.73 nmol/L across treatment period from Day 28 until Day 168 will be analysed as mentioned in the Section 5.1.2 for both ITT and PP population.

*Note: Castration level is defined as the observed percentage of participants who have T concentrations <0.5 ng/mL (1.73 nmol/L) at all scheduled visits.*

Descriptive statistics with proportion, its Clopper-Pearson confidence interval (CI) and absolute frequencies.

5. Proportion of participants achieving castration level with serum T <0.2 ng/mL or 0.6394 nmol/L across treatment period from Day 28 until Day 168 will be analysed as mentioned in Section 5.1.2 for both ITT and PP population.

6. Time to T levels falling below castration level (<0.5 ng/mL [1.73 nmol/L]) for the first time. First time castrate serum level (<0.5 ng/mL [1.73 nmol/L]) will be defined as the analysis event. Analysis will be done from Day 1 to the end of the study.

The following censoring rules will be used for this analysis:

- Patients who did not achieve castrate serum T levels with central lab during the study period will be censored at their last serum T level assessment.
- Patients who leave the trial without achieving castrate serum T levels will be censored at their last serum T level assessment.

7. Time to (first) overstep of T castration level after achieving castration will be analysed using the Kaplan-Meier method.

First time overstep of T castration level will be defined as the analysis event. Analysis will be done from the day of achieving castration T level to the end of the study. Only patients who achieved castration serum T levels will be analysed for both ITT and PP Population. Day of achieving castration T level will be defined as Day 1 for this analysis.

The following censoring rules will be used for this analysis:

- Patients with stable T level will be censored at their last available measure.
- Patients who fail to maintain castration T level will be censored at the day of failure.
- Patients who leave the trial for reasons other than a non-castrate serum T level will be censored at their last serum T level assessment.

*Note: Overstep of T castration level is defined as the first instance of T levels being above castration level after a patient has achieved castration.*

8. Time for serum T levels to be > 0.5 ng/mL after final, Day 168 injection will be analysed using the Kaplan-Meier method.

First time noncastrate serum T levels will be defined as the analysis event. Analysis will be done from Day 168 to the end of the observation. Only patients with castrate serum T levels at Day 168 will be analysed for both ITT and PP Population.

The following censoring rules will be used for this analysis:

- Patients who achieve and maintain castrate serum T levels with central lab from Day 168 through the end of the study period will be censored at their last serum T level assessment.
- Patients who leave the trial for reasons other than a non-castrate serum T level will be censored at their last serum T level assessment.

---

Document:

C:\ProgramData\activePDF\Temp\DocConverter\API\Input\\$651f4dc0b253\$FE3041C5883446E892B20AB6D3F0E1BD.docx

Author: [name]

Version and Date: Version 1.0, 21 Apr 2023

Page 60 of 66

9. Proportion of participants achieving castration level for LH (LH <1.1 U/L) at Day 28  
Descriptive statistics with proportion, will be analysed as mentioned in Section 5.1.2 for both ITT and PP population.
10. Proportion of participants with effective LH castration level across treatment period from Day 28 until Day 168. Descriptive statistics with proportion, will be analysed as mentioned in Section 5.1.2 for both ITT and PP population.
11. Time to LH levels falling below castration level (LH <1.1 U/L) for the first time will be analysed using the Kaplan-Meier method.  
First time LH levels falling below castration level (LH <1.1 U/L) will be defined as the analysis event. Analysis will be done from Day 1 to the end of the study.  
The following censoring rules will be used for this analysis:
  - Patients who did not achieve castration LH level during the study period will be censored at their last LH level assessment.
  - Patients who leave the trial without achieving castration LH level will be censored at their last LH level assessment.
12. Time to (first) overstep of LH castration level after achieving castration will be analysed using the Kaplan-Meier method. First time overstep of LH castration level will be defined as the analysis event. Analysis will be done from day of achieving castration LH level to the end of the study. Only patients who achieved castration LH level will be analysed for both ITT and PP Population. Day of achieving castration LH level will be defined as Day 1 for this analysis.  
The following censoring rules will be used for this analysis:
  - Patients with stable LH level will be censored at their last available measure.
  - Patients who leave the trial for reasons other than a non-castrate serum T level will be censored at their last LH assessment.
13. Changes from baseline in PD parameters over time will be analysed as mentioned in Section 5.1.2 for both ITT and PP Population.
14. Confirmed PSA Response Rate will be analysed as mentioned Section 5.1.2 for both ITT and PP Population  
*Note: Confirmed PSA Response rate is defined as patients who have a > 50% reduction at day 14 followed with confirmation at day 28*
15. PSA Response Rate at day 28 will be analysed as mentioned Section 5.1.2 for both ITT and PP Population
16. Number of participants with a PSA response of ≥50% reduction at the Day 168 visit will be analysed as mentioned in Section 5.1.2 both ITT and PP Population.
17. Number of participants with PSA response of ≥80% reduction at the Day 168 visit will be analysed as mentioned in Section 5.1.2 for both ITT and PP Population.
18. Percent change from baseline in serum PSA concentration at each visit will be analysed as mentioned Section 5.1.2 for both ITT and PP Population.

---

Document:

C:\ProgramData\activePDF\Temp\DocConverter\API\Input\\$651f4dc0b253\$FE3041C5883446E892B20AB6D3F0E1BD.docx

Author: [name]

Version and Date: Version 1.0, 21 Apr 2023

Page 61 of 66

19. Mean serum PSA concentration at each visit will be analysed as mentioned Section 5.1.2 for both ITT and PP Population.
20. PSA Levels at each visit will be analysed as mentioned Section 5.1.2 for both ITT and PP Population
21. Mean nadir PSA up to Day 168. To analyse this, for each subject the lowest PSA result will be taken from all collected PSA data up to Day 168 and the descriptive statistic of the lowest PSA level recorded during that time will be presented for both ITT and PP Population.
22. Time to nadir PSA level will be analysed as mentioned Section 5.1.2 for both ITT and PP Population.
23. Percent change from baseline in Serum LH concentration at each visit will be analysed as mentioned Section 5.1.2 for both ITT and PP Population
24. Mean serum LH concentration at each visit will be analysed as mentioned Section 5.1.2 for both ITT and PP Population.
25. LH Levels at each visit will be analysed as mentioned Section 5.1.2 for both ITT and PP Population.
26. Mean serum T concentration at each visit will be analysed as mentioned Section 5.1.2 for both ITT and PP Population.
27. Percent change from baseline in Serum FSH concentration at each visit will be analysed as mentioned Section 5.1.2 for both ITT and PP Population
28. Mean serum FSH concentration at each visit will be analysed as mentioned Section 5.1.2 for both ITT and PP Population.
29. FSH Levels at each visit will be analysed as mentioned Section 5.1.2 for both ITT and PP Population.

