### 2.1.2 Secondary Objectives

The secondary efficacy objectives of the study comprise the following:

- To assess the efficacy of teverelix TFA in terms of ability to suppress serum T levels to below castration level (<0.2 ng/mL or 0.6934 nmol/L) at Day 28
- To assess the efficacy of teverelix TFA in terms of ability to suppress serum T levels to below castration level (<0.5 ng/mL or 1.73 nmol/L) at Day 42
- To assess the efficacy of teverelix TFA in terms of ability to suppress serum T levels to below castration level (<0.2 ng/mL or 0.6934 nmol/L) at Day 42
- To assess the efficacy of teverelix TFA in terms of ability to suppress serum T levels to below castration level (<0.5 ng/mL or 1.73 nmol/L) across treatment period from Day 28 until Day 168
- To assess the efficacy of teverelix TFA in terms of ability to suppress serum T levels to below castration level (<0.2 ng/mL or 0.6934 nmol/L) across treatment period from Day 28 until Day 168
- To assess the efficacy of teverelix TFA in terms of ability to maintain suppression of serum T levels below castration level (<0.5 ng/mL or 1.73 nmol/L) over time during Stage 2 (maintenance-dose period) of the study
- To assess the efficacy of teverelix TFA in terms of ability to maintain suppression of serum T levels below castration level (<0.2 ng/mL or 0.6934 nmol/L) over time during Stage 2 (maintenance-dose period) of the study
- To assess the time taken to achieve serum T levels below castration level (<0.5 ng/mL or 1.73 nmol/L)
- To assess the time taken to achieve serum T levels below castration level (<0.2 ng/mL or 0.6934 nmol/L)
- To assess the time taken to achieve serum T levels above castration level ( $\geq 0.5$  ng/mL or 1.73 nmol/L) following the final, Day 168 injection of teverelix TFA.
- To delineate the pharmacokinetics (PK) profile of teverelix TFA
- To assess the effects of teverelix TFA on:
  - PSA
  - T
  - FSH
  - LH
- To assess the predictive effect for new cardiovascular (CV) events of cardiac biomarkers:
  - N-terminal pro-B-type natriuretic peptide (NTproBNP)
  - D-dimer
  - C-reactive protein (CRP)
  - high-sensitivity troponin (hsTn)

The safety objectives of the study comprise the following:

- To assess the safety of teverelix TFA in terms of
  - Local tolerability (injection site reaction [ISRs])
  - Systemic tolerability (AEs, vital signs, electrocardiograms (ECG), Holter monitoring (subset of 30 subjects in group 2 only) and laboratory parameters)

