## List of Secondary Analysis Endpoints to be Included in the Study Results:

1. Proportion of participants achieving castration level with serum T <0.2 ng/mL at Day 28.  
Percentage of participants who have T concentrations <0.2 ng/mL at the end of Stage 1 (Day 28).
2. Proportion of participants achieving castration level with serum T <0.5 ng/mL at Day 42.
3. Proportion of participants achieving castration level with serum T <0.2 ng/mL at Day 42.
4. Proportion of participants achieving castration level with serum T <0.5 ng/mL across treatment period from Day 28 until Day 168  
Note: Defined as the observed percentage of participants who have T concentrations <0.5 ng/mL (1.73 nmol/L) at all scheduled visits.
5. Proportion of participants achieving profound castration level(<0.2 ng/mL) across treatment period from Day 28 until Day 168.
6. Time to T levels falling below castration level (<0.5 ng/mL [1.73 nmol/L]) for the first time.
7. Time to (first) overstep of T castration level after achieving castration.  
Note: Overstep of T castration level is defined as the first instance of T levels being above castration level after a patient has achieved castration.
8. Time for serum T levels to be > 0.5 ng/mL after final, Day 168 injection.
9. Proportion of participants achieving castration level for LH (LH <1.1 U/L) at Day 28
10. Proportion of participants with effective LH castration level across treatment period from Day 28 until Day 168
11. Time to LH levels falling below castration level (LH <1.1 U/L) for the first time
12. Time to (first) overstep of LH castration level after achieving castration.
13. Changes from baseline in PD and PK parameters over time
14. Confirmed PSA Response Rate
15. PSA response rate at day 28
16. Number of participants with a PSA response of ≥50% reduction at the Day 168 visit
17. Number of participants with PSA response of ≥80% reduction at the Day 168 visit
18. Percent change from baseline in serum PSA concentration at each visit
19. Serum PSA concentration at each visit
20. PSA levels at each visit
21. Mean nadir PSA up to Day 168
22. Time to nadir PSA level
23. Percent change from baseline in Serum LH concentration at each visit
24. Serum LH concentration at each visit

Document:

C:\ProgramData\activePDF\Temp\DocConverter\API\Input\\$651f4dc0b253\$FE3041C5883446E8  
92B20AB6D3F0E1BD.docx

Author: [name]

Version and Date: Version 1.0, 21 Apr 2023

Page 31 of 66

25. LH levels at each visit

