**4.2.6 Clinical Laboratory Evaluations**

Fasted (>8 hours) blood samples for haematology and biochemistry tests, as well as a urine sample for urinalysis, will be collected for safety monitoring at screening, baseline, Day 28, all dosing visits of Stage 2 and the follow-up visit. For safety analysis, a blood volume of approximately 8 mL will be drawn per timepoint. Full details of blood volumes drawn during the study are documented in the Laboratory Manual.

All laboratory results are standardized to Système International (S.I) units.

An overview of measured parameters is given in Table 14.

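### SAP 6.8.2 prints a mistyped nmol/L equivalent (0.6394 instead of 0.6934) beside the correct 0.2 ng/mL cut-off in three secondary analyses

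*SAP*

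**What the plan says.** SAP 6.8.2 lists the secondary efficacy analyses. Three of them use the lower testosterone cut-off:

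- Item 1: "serum T <0.2 ng/mL or 0.6394 nmol/L at Day 28"
- Item 3: "serum T <0.2 ng/mL or 0.6394 nmol/L at Day 42"
- Item 5: "serum T <0.2 ng/mL or 0.6394 nmol/L across treatment period from Day 28 until Day 168"

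SAP 2.1.2 pairs the same ng/mL cut-off with a different SI figure: "below castration level (<0.2 ng/mL or 0.6934 nmol/L) at Day 28". The protocol objectives, in both the synopsis and section 2, also give 0.6934 nmol/L.

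The SAP list of secondary endpoints in 4.1.2 gives no SI value for this cut-off: "Proportion of participants achieving castration level with serum T <0.2 ng/mL at Day 28". The protocol endpoint lists (synopsis and 8.1.4) likewise use ng/mL only. SAP 7.1, which records changes from the protocol analyses, mentions no change of cut-off.

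**The concern.** Section 6.8.2 is where the SAP specifies the analyses, so a threshold printed there defines who is counted. Each of the three items joins two figures with the word "or" as though they were equivalent, but they are not, and the SAP does not say which governs. The results at stake are the three proportions with testosterone below 0.2 ng/mL: at Day 28, at Day 42, and across Day 28 to Day 168.

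Item 5 is the most exposed. If the all-scheduled-visits rule stated under item 4 also applies to it, one value in the disputed band at any visit would change a participant's status. SAP Table 7 schedules central testosterone at six visits in that period (Days 28, 35, 42, 84, 126 and 168).

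**Working it through.** **Inputs**

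- Primary cut-off, SAP 6.8.1: "Proportion of participants achieving castration level with serum T <0.5 ng/mL or 1.73 nmol/L at Day 28".
- Lower cut-off as defined in SAP 2.1.2 and the protocol objectives: 0.2 ng/mL, 0.6934 nmol/L.
- Lower cut-off as printed in SAP 6.8.2 items 1, 3 and 5: 0.2 ng/mL, 0.6394 nmol/L.

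**Step 1. Conversion factors implied by the documents** (nmol/L per ng/mL)

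- From the primary cut-off: 1.73 / 0.5 = 3.460. Since 1.73 is rounded, it could stand for 1.725 to 1.735, which gives 3.45 to 3.47.
- From the objectives: 0.6934 / 0.2 = 3.467, inside that range.

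**Step 2. Try to reproduce the printed figure**

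| Factor | 0.2 ng/mL in nmol/L |
|---|---|
| 3.45 | 0.690 |
| 3.460 | 0.692 |
| 3.467 | 0.6934 |
| 3.47 | 0.694 |

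The range is 0.690 to 0.694. It contains 0.6934. No variant gives 0.6394.

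**Step 3. Convert the printed figure back**

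- 0.6394 / 3.467 = 0.1844 ng/mL
- 0.6394 / 3.460 = 0.1848 ng/mL
- Over factors 3.47 to 3.45: 0.1843 to 0.1853 ng/mL

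**Step 4. Size of the discrepancy**

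- 0.6934 − 0.6394 = 0.054 nmol/L
- 0.054 / 0.6934 = 7.8%

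**Step 5. What it would do to a participant**

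A value of 0.19 ng/mL is 0.19 × 3.467 = 0.659 nmol/L. That is below 0.2 ng/mL (responder) but not below 0.6394 nmol/L (non-responder). With the 50 evaluable Group 2 participants planned, each person reclassified would move a proportion by 1/50 = 2 percentage points. The documents do not say how many values fall in the band, so the effect on any proportion cannot be computed.

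**Step 6. Deliberate change or extraction fault?**

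SAP 7.1 records no new cut-off. The same wrong digits occur in three items, while 1.73 is printed correctly in items 2 and 4 between them. A transposition copied into three items fits best.

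**The case against.** The strongest reply is that nothing would go wrong in practice. Each item states the correct 0.2 ng/mL first, with nmol/L trailing as an equivalent. The endpoint lists give this cut-off in ng/mL only, SAP 4.1.2.1 names local testosterone in ng/mL, and item 8 and the missing-data examples in SAP 6.8.3 use ng/mL alone. A programmer working in ng/mL gets the right answer. This stands, and it limits the point to a wrong equivalent beside a right threshold.

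A reader might infer more from SAP 4.2.6: "All laboratory results are standardized to" SI units, so testosterone would be analysed in nmol/L and participants misclassified. The documents do not support that. The sentence belongs to the safety laboratory section, which covers haematology, biochemistry and urinalysis, and its Table 14 does not list testosterone. Testosterone is treated as an efficacy and pharmacodynamic variable in SAP 4.1 and 4.3.9. The output shells, which might settle the unit, are not among the documents.

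The consequences are also bounded. Protocol 8.1.4 makes the secondary analyses exploratory and descriptive, and no decision rule uses 0.2 ng/mL. If the wrong figure were used, it would lower the proportion counted as profoundly castrate, so it could not flatter the drug. Reporting precision for testosterone is not stated. Assuming results to 0.01 ng/mL, only a reading of 0.19 would change class; assuming 0.1 ng/mL, none would.

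What survives is that three analysis definitions contradict themselves and the SAP has no rule for which figure prevails.

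**Conclusion.** The printed 0.6394 nmol/L is an error for 0.6934 nmol/L in SAP 6.8.2 items 1, 3 and 5. This rests only on the documents' own figures and holds for every conversion factor they allow. The mistyped value is about 0.184 ng/mL, 7.8% below the intended cut-off. The 7.8% describes the cut-off; it is not a shift in any proportion.

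Misclassification is possible but not indicated. It needs two things the documents do not show: classification programmed on the nmol/L figure, and observed values from about 0.184 to just under 0.200 ng/mL. The 0.5 ng/mL primary endpoint, the stopping rules at 2 ng/mL and the FDA-recommended Kaplan-Meier analysis at 0.5 ng/mL do not use this cut-off. Severity is minor.

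**What to change.** In SAP 6.8.2 items 1, 3 and 5, replace 0.6394 with 0.6934 nmol/L. Add one sentence stating that responder classification uses the ng/mL value and that nmol/L figures are for information. That sentence also settles the small rounding gap at the primary cut-off, where 0.5 × 3.467 = 1.7335 and the documents print 1.73. Check that the output shells and programs carry the same threshold.

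The cost is three figures and one sentence. SAP 7.2 allows no change to Version 1.0 after database lock, so the correction belongs before lock. If lock has passed, the clinical study report should state which threshold was applied.
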